1. PURPOSE OF THIS SURVEILLANCE

This post-marketing surveillance (hereinafter referred to as "the PMS") is to be conducted for a medical device prescribed in Paragraph 1 in Article 14 of the Pharmaceutical Affairs Law (Law No. 145, August 10, 1960, hereinafter referred to as "PAL") by a marketing approval holder or restrictive foreign approval holder of medical device prescribed in the standard for post-marketing surveillance and post-marketing study (excluding those set forth in Ministerial Ordinance Concerning the Standards for Executing Clinical Tests on Medical Devices, Ministerial Ordinance No. 36, March 23, 2005), which is part of the standard established by the Minister of Health, Welfare and Labor set forth in Paragraph 4 in Article 14-4 and Paragraph 4 in Article 14-6 (including when applied mutatis mutandis to Paragraph 4 in Article 19 of PAL). The objectives of the PMS are to observe the frequency, type, and degree of device deficiency to assure the safety of the new medical device as well as to collect information on evaluation of the efficacy and safety for reevaluation.

The PMS is to be conducted in accordance with Ministerial Ordinance Concerning the Standards for Post-marketing Surveillance and Tests of Medical Devices (Ministerial Ordinance No. 36, March 23, 2005, hereinafter referred to as "Good Post-marketing Study Practice: GPSP").

2. ELIGIBILITY AND PLANNED REGISTRATION

2.1 Target Patient Population

Based on GPSP regulation, general patient population with ischemic heart disease who are eligible for treatment with XIENCE Xpedition Everolimus-Eluting 2.25mm Stent (Approval Number: 22500BZX00309000; Approval Date: May 20, 2014), will be registered, with no particular inclusion/exclusion criteria, and may be eligible for angiographic follow-up at eight months and clinical follow-up at one year.

2.3 Number of Patients to be Registered

The goal is to register about 100 patients from approximately 10 sites.

The XIENCE Xpedition 2.25 mm stent is identical to the stent of the XIENCE PRIME SV Everolimus-Eluting Coronary Stent System (Approval No. 22500BZX00070000) which is currently under use result surveillance. The sample size is calculated based on the following statistical hypothesis and assumptions: The in-stent late loss = 0.2 mm (SD = 0.5 mm) for both the XIENCE PRIME SV stent and the XIENCE Xpedition 2.25 mm stent; the QCA follow-up rate of the XIENCE PRIME SV PMS (300 patients) = 75% (225 lesions); one-tailed test with alpha = 0.05; power = 90%; non-inferiority delta = 0.195 mm. Given the above assumptions, 75 patients are needed to demonstrate the non-inferiority to the XIENCE PRIME SV stent. Assuming drop-outs, approximately 100 patients are considered a target sample size which ensures the effectiveness of the XIENCE Xpedition 2.25 mm stent.

3. **PMS DURATION**

Patients will be followed by 5 years. After signing the contract with each sites and the enrollment can be started, the target duration of patient registration for the PMS will be by September 5th, 2015.

Annual reports will be submitted to PMDA every year. After the re-submission, data will continue to be collected until 5 year follow-up is complete for all patients.

Patient data from the following time points will be collected

- Baseline (before procedure)
- Procedure
- Post-Procedure through discharge
- 8 months follow-up (follow-up angiogram)
- 1 year post-procedure (site visit is recommended)
- 2 year post-procedure (site visit/telephone contact)
- 3 year post-procedure (site visit/telephone contact)
- 4 years post-procedure (site visit/telephone contact)
- 5 years post-procedure (site visit/telephone contact)

4. **PATIENT TREATMENT**

Patient treatment strategy should be determined by the physicians based on standard PCI procedure at each of the sites. Physicians should review the latest updated IFU, and carefully consider contraindications, warnings, and precautions when considering patient treatment.

Although dual antiplatelet management is ultimately determined by physicians, enrolled patients will be encouraged to receive adjunctive antiplatelet therapy consisting of an indefinite duration of aspirin in addition to a required minimum of 12 months of thienopyridine (clopidogrel, ticlopidine, etc.). It is recommended that physicians review the requirements of the most recent thienopyridine IFU before treating patients.

5. OBSERVATION ITEMS AT EACH TIME POINT

5.1 **Baseline Information**

1) Patient Basic Information

- Index Procedure Date (Date of Registration)
- Birth year and month
- Implant of XIENCE Xpedition 2.25mm stent (Only basic information, non-implant stent form and device deficiency form must be completed in the case all XIENCE Xpedition 2.25mm stents are failed to implant)
- Gender
- Height
- Weight
- Admission and Discharge dates

2) Cardiac Status at the Index Procedure and Cardiac History

- Cardiac Status (Symptom of ischemia) at the Registration
- History of Myocardial Infarction
- Previous CABG
- Previous PCI

3) Risk Factors

- Family History of Premature Coronary Artery Disease
- Smoking History
- Hypertension
- Dyslipidemia
- Diabetic Mellitus
- Renal Disease
- History of Stroke
- History of Major Bleeding
- Unstable Arrhythmia
- Chronic Anticoagulant Therapy

4) **Pre-Procedure ECG**

5) **Pre-Procedure Cardiac Enzyme and Creatinine**

- Cardiac Enzyme
 - o CK
 - CK-MB (If MI is suspected then must be measured per site standard practice)
- Serum Creatinine

6) **Pre-Procedure Antiplatelet**

- Aspirin
- Clopidogrel
- Ticlopidine
- Cilostazol

5.2 **Procedure Information**

1) General Information

- Physician Name
- Procedure Start Time (Insertion of Guide Catheter)
- Procedure End Time (Removal of Guide Catheter)
- Access Site
- Number of Diseased Vessels
- Number of Treated Lesions
 - Treated only by XIENCE PRIME (Target Lesion)
 - Treated by XIENCE PRIME and Other Stent (Target Lesion)
 - Treated only by other devices (Non-target Lesion)
- LVEF

2) Lesion Information

Angiographic corelab analysis data will be adopted when it is applicable.

- Lesion Number
- Target or Non-target Lesion
- AHS Lesion Segment Number
- Lesion Type (de novo or restenosis)
- Complex Lesion
- Thrombectomy
- Lesion Preparation (pre-dilatation)
- Post-dilatation
- Use of Bailout Stent
- Total Number of Stents Implanted
- Post-procedure within stent after Post-dilatation
- Other concomitantly-used medical device

3) Bifurcated Lesion (If applicable)

- Side Branch AHA Segment
- Bifurcation Lesion Type
- Technique Used
- Kissing Balloon

4) Lesion Visual Assessment (Pre and Post Procedure)

Angiographic corelab analysis data will be adopted when it is applicable.

- Lesion Length
- Reference Vessel Diameter
- %DS
- TIMI Flow

5) Stent Information

- Stent information must be recorded per lesion
 - o Length and Diameter
 - Deployment Pressure
 - Successful Deployment
 - Deployed Vessel (main vessel or side branch)

5.3 **Post Procedure Information**

1) **Post-Procedure ECG**

2) **Post-Procedure**

- Cardiac Enzyme
 - o CK
 - CK-MB (If MI is suspected then must be measured per site standard practice)

5.4 **Post-Procedure (Maintenance) Antiplatelet**

- Type
- Start Date
- Daily Dose
- Termination or Continuation

5.5 8 Months Follow-up

1) General Information

- Contact Method
- Contact Date
- Reportable adverse event since the last follow-up
- Change or termination of antiplatelet therapy
- Device Deficiency
- Follow-up Angiogram
- Ischemic Symptoms
- Revascularization

2) Angiographic Information

Angiographic corelab analysis data will be adopted when it is applicable.

- Lesion Length (if restenosis exist)
- Reference Vessel Diameter
- %DS

5.6 1~5 Years Follow-up (Every Year)

- Contact Method
- Contact Date
- Reportable adverse event since the last follow-up
- Change or termination of antiplatelet therapy
- Device Deficiency

5.7 Unscheduled Visit (Reportable AE related)

Complete AE form(s) if a patient visits the hospital with reportable adverse event(s).

5.8 Device Deficiency

- Date of deficiency
- Type of deficiency
- Did the device deficiency result in an adverse event?
- Description of deficiency/comment
- Product details (lot, serial numbers, etc.)

5.9 Adverse Event (Reportable Event)

Record the following adverse events (including procedural complications) and their details.

- All Coronary artery related adverse events
 - Ischemic symptoms, evidences, including test results
 - Diagnostic angiogram
 - o Revascularization
- All serious adverse events*
- All events for which relationship to XIENCE Xpedition 2.25mm stent cannot be ruled out
- All other adverse events related to taking antiplatelet medication(s)
- * Serious adverse event: death, life-threatening, hospitalization (initial or prolonged), disability or permanent damage, congenital anomaly/birth defect, other serious (investigator's judgment).

Evaluate and record relationship of the above adverse events to the Device, procedure, and antiplatelet therapy, as well as the outcome of each event. If the event is an SAE, record the reason for considering the event as an SAE.

6. **EVALUATION ITEMS**

6.1 Important Evaluation Items

Important evaluation items in this PMS are;

- 1) Stent Thrombosis
- 2) Adverse events caused by Anti-platelet Medications
- 3) Longitudinal stent deformation

6.2 Other Evaluation Items

Other evaluation items will be per standard drug eluting studies.

7. DATA ANALYSIS

7.1 Angiographic Core-Lab

Angiographic data at the index procedure and 8 months follow-up will be analyzed by Core-lab for lesion characteristics and quantitative coronary angiography (QCA) analysis.

Core-lab: KIC Co., Ltd Core-lab Department [name]

XIENCE Xpedition 2.25mm stent JAPAN PMS Execution Overview

7.2 Independent Review of Adverse Events

Objective review of adverse events (Stent Thrombosis, Cardiac Death, Myocardial Infarction, and TLR/TVR) will be conducted by a third party (medical professional) up to 3 years post index procedure. These events will be reviewed based on ARC definition. QCA results from angiographic core-lab will be provided to the reviewer as necessary.

7.3 Analysis of Results

Collected data will be analyzed and Annual Report will be submitted according to "Survey Report on new medical device usage" (Japan Pharmaceutical and Food Safety Bureau Notice 1224, no. 4, dated December 24, 2010). Subgroup analyses will be conducted as necessary to evaluate safety and efficacy of the device, and included in the resubmission report.

The XIENCE Xpedition 2.25 mm stent is composed of the stent identical to the stent of the XIENCE PRIME SV Stent approved on March 7, 2013. Therefore, the data collected from the PMS will be pooled with data collected from the ongoing XIENCE PRIME SV PMS for analysis.

1.1. Objectives

This is a post-marketing use result survey (hereinafter referred to as "Survey") conducted per the standards required by the Minster of Health, Labor and Welfare provided in the standards for post-marketing surveillances and studies [except for those defined in the Ministerial Ordinance on Good Clinical Practice for Medical Devices (MHLW Ordinance No. 36, 2005)] based on Paragraph 4, Article 14-4 and Paragraph 4, Article 14-6 (including application mutatis mutandis per Article 19-4) of the Pharmaceutical Affairs Law (Law No. 145, 1960, hereinafter referred to as "PAL") by the Marketing Authorization Holder or accredited foreign manufacturer of a medical device defined in Paragraph 1, Article 14 of the PAL. The purpose of the Survey is to know the frequency and status of adverse device effects and adverse events in order to assure the safety of the new medical device, and to collect efficacy and safety information to be evaluated for repeat review by PMDA. The Survey is conducted per the Ministerial Ordinance on Good Post-marketing Surveillance Practice (MHLW Ordinance No. 38, 2005, hereinafter referred to as "GPSP Ordinance").

1.2. Patients of the Surveillance

[XIENCE PRIME SV Everolimus-eluting Stent]

Based on the GPSP Ordinance, the Survey enrolls patients with ischemic heart disease potentially indicated for treatment with the XIENCE PRIME Everolimus-eluting Stent (Approval No. 22400BZX00145000, April 6, 2012, hereinafter referred to as "Surveillance Device") without any predefined specific inclusion or exclusion criteria. As a general rule, enrolled patients must be treated with XIENCE PRIME as part of treatment given in each survey site in the real-world setting and must be available for angiographic follow-up at 8 months and clinical follow-up at 1 year.

In addition to the patients who will first be enrolled in this Surveillance, patients who have been participating in a pre-market clinical trial of the XIENCE PRIME SV stent (the AVJ-09-385 trial: A Clinical Evaluation of the AVJ-09-385 Coronary Stent System in Japanese Population) are included in the subject. The patients enrolled in the AVJ-09-385 trial were to be followed for five years, and the patient follow-up had been performed as part of a pre-market study until the marketing approval date. Upon consultation with the PMDA, it was agreed that the trial be continued as a Post Marketing Surveillance after marketing approval, and the trial (follow-up) completion date be the marketing approval date. Based on the agreement, the AVJ-09-385 trial was continued as the Post Marketing Surveillance upon marketing approval.

[XIENCE Xpedition 2.25 mm Everolimus-eluting Stent]

Ver.2.0

Based on the GPSP Ordinance, the Survey enrolls patients with ischemic heart disease potentially indicated for treatment with the XIENCE Xpedition 2.25 mm Everolimus-eluting Stent (Approval No. 22500BZX00309000, May 20, 2014, hereinafter referred to as "Surveillance Device") without any predefined specific inclusion or exclusion criteria. As a general rule, enrolled patients must be treated with XIENCE PRIME as part of treatment given in each survey site in the real-world setting and must be available for angiographic follow-up at 8 months and clinical follow-up at 1 year.

1.3. Planned Sample Size

[XIENCE PRIME SV Everolimus-eluting Stent]

The target sample size of the Surveillance is approximately 300 patients from approximately 30 sites, including 62 patients continuing from the AVJ-09-385 trial.

MACE (composite of cardiac death, myocardial infarction and ischemia-driven target lesion revascularization) rate of this surveillance is expected to be 15%, based on past trials. For 300 patients, half of 95% confidence interval of MACE rate of 15% is 4.2%. This is 28% of expected MACE rate of 15%. This range will be enough to evaluate safety and efficacy of XIENCE PRIME SV in real world practice in Japanese hospitals.

[XIENCE Xpedition 2.25 mm Everolimus-eluting Stent]

The target sample size of the Surveillance is approximately 100 patients from at least 5 sites. The stent component of the device is identical to the XIENCE PRIME SV Everolimus-eluting Stent (EES) which is currently under use result surveillance (Marketing Approval No. 22500BZX00070000). Provided that the in-stent LL of both the XIENCE PRIME SV EES and the Surveillance Device is 0.2mm with standard deviation of 0.5 mm, the QCA follow-up rate of 300 subjects in the XIENCE PRIME SV EES use result surveillance is 75% (225 lesions), $\alpha = 0.05$ (one-sided), power = 90%, and non-inferiority margin = 0.195 mm, 75 patients is required to demonstrate the non-inferiority to the XIENCE V PRIME SV EES. Considering drop-put, approximately 100 subjects can be a target sample size to guarantee efficacy of the device.

1.4. Treatment of Patients

[XIENCE PRIME SV Everolimus-eluting Stent]

The treatment strategy will be determined by the physician according to the healthcare facility's standard of care for interventional cardiology.

It is recommended that each enrolling physician review the most recently updated IFU and assess the

contraindications, warnings, and precaution sections for treating potential patients.

Although antiplatelet medication is ultimately determined by physicians, enrolled patients will be encouraged to receive adjunctive antiplatelet therapy consisting of an indefinite duration of aspirin, along with required a minimum of 6 months of thienopyridine (clopidogrel, ticlopidine, etc.). And in the Xience Prime IFU, enrolled patients will receive antiplatelet therapy required a minimum of 12 months of thienopyridine. It is recommended that physicians review the requirements of the most recent thienopyridine IFU before treating patients. Required lab assessments and clinical observations to evaluate thienopyridine side effects must be conducted per its approved IFU.

[XIENCE Xpedition 2.25 mm Everolimus-eluting Stent]

The treatment strategy will be determined by the physician according to the healthcare facility's standard of care for interventional cardiology.

It is recommended that each enrolling physician review the most recently updated IFU and assess the contraindications, warnings, and precaution sections for treating potential patients.

Although antiplatelet medication is ultimately determined by physicians, enrolled patients of low bleeding risk will be encouraged to receive adjunctive antiplatelet therapy consisting of an indefinite duration of aspirin in addition to a required minimum of 12 months of thienopyridine (clopidogrel, ticlopidine, etc.) per product IFU. It is recommended that physicians review the requirements of the most recent thienopyridine IFU before treating patients. Laboratory tests and clinical observations required for evaluating adverse reactions to thienopyridine medication should be performed in accordance with the IFU.

2. Definitions of Analysis Populations and Acronyms

2.1. Definitions of Analysis Populations

No	Term	Definition
1	Surveillance Period	[XIENCE PRIME SV EES]
		From March 7, 2013 to December 31, 2019
		[XIENCE Xpedition 2.25 mm EES]
		From July 1 to March 31, 2021
2	Data Lock Date	Data will be locked at the following dates for periodical reporting:
		1 st Data Lock Date : Sep/05/2013
		2 nd Data Lock Date : Sep/05/2014
		3 rd Data Lock Date : Sep/05/2015
		4 th Data Lock Date : Sep/05/2016
		5 th Data Lock Date : Sep/05/2017
		6 th Data Lock Date : Sep/05/2018
		7 th Data Lock Date : Sep/05/2019
		Each analysis will include the cases of which case cards have
		been frozen before the data are locked.
3	Case with Case Card	A case of which case card data has been fixed.
	collected	
4	XP_SV Arm	The group of patients with Case Card collected who were treated
		with the XIENCE PRIME SV EES.
5	XX_SV Arm	The group of patients with Case Card collected who were treated
	_	with the XIENCE Xpedition 2.25 mm EES.

Analysis will be performed for the XP_SV Arm and the XX_SV Arm each and for all enrolled patients.

2.2. Definition of Term

No	Term	Definition
1	Dual Antiplatelet	Combined use of aspirin and thienopiridine (e.g. clopidogrel,
	Therapy	ticlopidine).

2.3. Acronyms

No	Acronym	Description
1	CABG	Coronary Artery Bypass Grafting
2	СТО	Chronic Total Occlusion
3	eGFR	Estimated Glomerular Filtration Rate
4	LAD	Left Anterior Descending Artery

Ver.2.0

uniouni	<english for="" only="" reference="" translation=""> Ver.2.0</english>		
No	Acronym	Description	
5	LCX	Left Circumflex Artery	
6	LMT	Left Main Trunk	
7	LVEF	Left Ventricular Ejection Fraction	
8	PCI	Percutaneous Coronary Intervention	
9	POBA	Plain Old Balloon Angioplasty	
10	Q1	First Quartile	
11	Q3	Third Quartile	
12	RCA	Right Coronary Artery	
13	SVG	Saphenous Vein Graft	
14	TLR	Target Lesion Revascularization	
15	TVR	Target Vessel Revascularization	

Ver.2.0

3. Analysis Methods

3.1. Statistical Analysis Environment

Statistical analysis software: SAS Windows Edition, Version 9.2 or higher, SAS Institute Inc.

3.2. Calculation Methods

Data Item	Calculation Method etc.
Summary Statistic	Mean value, SD, number of sample, median, Q1, Q3, minimum value, maximum
(continuous variable)	value, and 95% CI of mean value will be calculated.
	Number of sample: To be represented in integer. Mean, SD, median, Q1, Q3: To be represented to one decimal below the data for calculation. Minimum, maximum: To be represented in the same decimal as the data for calculation.
CI of Mean Values	CI based on t distribution will be calculated:
	$CI = \overline{x} \pm t_{(1-\alpha/2;n-1)} \frac{S}{\sqrt{n}}$
Summary Statistic	Incidence (%), count of events (numerator), analysis population (denominator) and
(incidence)	95% CI of mean value will be calculated.
CI of Occurrences	Exact CI based on Clopper-Pearson method will be calculated:
	$\pi_{\rm L} = \frac{v_2}{v_1 + v_1 E_{\rm ex}[v_1 + v_2]}$ $v_1 = 2(n - x + 1), v_2 = 2x$
	$\pi_{\rm L} = \frac{v_2}{v_2 + v_1 F_{\alpha/2}[v_1, v_2]} v_1 = 2(n - x + 1), v_2 = 2x$ $\pi_{\rm U} = \frac{v_1 F_{\alpha/2}[v_1, v_2]}{v_2 + v_1 F_{\alpha/2}[v_1, v_2]} v_1 = 2(x + 1), v_2 = 2(n - x)$
Age (in years)	Actual age at procedure (enrollment) date will be calculated from year/month of birth (day will be deemed as 1 st day of the month).
Body Mass Index	BMI will be calculated from weight (kg) and height (cm):
	Body Mass Index = Weight (kg) / (Height [cm]/100) ²
Follow-up Time	8-month Follow-up: 8 months post procedure \pm 30 days
Window	1-year Follow-up: 1 year post procedure \pm 30 days
	2-year Follow-up: 2 years post procedure \pm 30 days
	3-year Follow-up: 3 years post procedure \pm 30 days
	4-year Follow-up: 4 years post procedure \pm 30 days
	51-year Follow-up: 5 years post procedure \pm 30 days
	Data collected outside time window can be used as data collected at respective follow-
	up time point if the quality of the data is confirmed as qualified.

4. Statistical Analysis Details

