4.1.2. Case Card Collected

Case card collected per binder will be aggregated by treatment group.

Table 2: Follow-up Rate

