4.4. Adverse Events

4.4.1. Adverse Events (Composite Endpoint)

The occurrence rates of adverse events (composite endpoint) at each occurrence time and follow-up time

point will be calculated.

Item

No	Timing of Onset	
1	Procedure date to procedure date ± 3 days	
2	4 days + procedure date to discharge date	
3	1 day + discharge date to 8MFU	
4	1day + 8MFU to 1YFU	
5	1day + 1YFU to 2YFU	
6	1day + 2YFU to 3YFU	
7	1day + 3YFU to 4YFU	
8	1day + 4YFU to 5YFU	

Table 18: Adverse Events (Composite endpoint, at each follow-up time point)

No	Data Item	
1	Target lesion failure [Cardiac death, Target vessel MI, Ischemia-driven TLR]	
2	Death + MI + Revascularization [Death, MI, Revascularization]	
3	Target vessel failure [Cardiac death, MI, Ischemia-driven TLR, Ischemia-	
	driven TVR (non-TLR)]	
4	Major adverse cardiac event (Cardiac death, All MI, Ischemia-driven TLR)	
5	Death or MI	
6	Cardiac death or MI	
7	Cardiac death or target vessel MI	

Breakdown of the data item will be provided in brackets [].

Adjudication of MI is based on the definition by WHO (SPIRIT III)

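### The SAP defines no at-risk denominator for event rates by follow-up interval, so late-band rates can print too low at interim locks; Table 18 bands 1 and 3 also overlap for early discharge

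*SAP*

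**What the plan says.** **Rate and population.** The incidence entry in SAP 3.2 reads "Incidence (%), count of events (numerator), analysis population (denominator) and" a 95% interval, computed by Clopper-Pearson. SAP 2.1 defines each arm (XP_SV, XX_SV) as the patients treated with that device who have a case card collected, which means "A case of which case card data has been fixed". Results are produced for each arm and for all enrolled patients. No at-risk set, band-specific denominator, censoring rule or time-to-event method appears in the SAP.

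**Locks.** SAP 2.1 lists yearly locks for periodic reports, the last being "7 th Data Lock Date : Sep/05/2019". Each analysis takes the cases whose cards were frozen before the lock. For Table 2, SAP 4.1.2 says "Case card collected per binder will be aggregated by treatment group".

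**Bands.** SAP 4.4.1 lists eight onset bands for Table 18. Band 1 is "Procedure date to procedure date ± 3 days". Band 2 runs from day 4 to discharge, band 3 from the day after discharge to the 8-month follow-up, and the later bands run on to year 5. SAP 4.4.2 (Table 19) reports by follow-up time point and lists no bands.

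**Calendar.** The XX_SV surveillance period is "From July 1 to March 31, 2021", with no year for the July date. In Protocol 3, "the target duration of patient registration for the PMS will be by September 5th, 2015", and collection continues until every patient has completed five years.

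**The concern.** A rate for an interval such as year 4 to year 5 describes patients only if its denominator is the set who could have had the event in that interval. SAP 3.2 points to a whole arm instead. At a periodic lock that arm includes patients who died or were lost earlier, and patients whose interval has not started or is still running.

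The dilution depends on how far each arm has been followed. XP_SV surveillance is scheduled to end on December 31 2019 and XX_SV on March 31 2021, so at a common lock XX_SV is less mature. Two arms with the same true late rate could print different rates, with the newer device looking better only because it is newer. The pooled column, which Protocol 7.3 and SAP 2.1 both call for, would mix the two stages.

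The band overlap is a separate and smaller matter: one early event after discharge can be counted in two rows of Table 18.

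**Working it through.** **1. The plan's own figure.** SAP 1.3 states "For 300 patients, half of 95% confidence interval of MACE rate of 15% is 4.2" percent. Clopper-Pearson for 45/300 gives 11.16% to 19.55%, a half-width of 4.20%, which is 28.0% of 15%. A Wald interval gives 4.04%. The stated figure reproduces as a patient-level exact interval, so patients are evidently the intended unit, although SAP 3.2 says events.

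**2. XX_SV, year 4-5 band, lock of September 5 2019.** Inputs from the documents: the lock date and the registration target of September 5 2015. Assumptions: uniform registration, nominal anniversaries, no attrition, every event up to the lock captured, constant hazard within the band, and a true band rate of 3.0%. The start of registration is varied because the July year is not given.

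For a July 1 2014 start there are 432 registration days. Patients registered by September 5 2014 (67 days) have completed the band: 67/432 = 15.5%. The other 365 days contribute (364 + 363 + ... + 0)/365 = 182 band-equivalents. Observed share = (67 + 182)/432 = 57.6%, and 3.0% x 0.576 = 1.7%.

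| Assumed start | Observed share of band time | 3.0% prints as |
|---|---|---|
| May 20 2014 (approval) | (109 + 182)/474 = 61% | 1.8% |
| July 1 2014 | 249/432 = 58% | 1.7% |
| January 1 2015 | 83.9/248 = 34% | 1.0% |
| July 1 2015 | 6.06/67 = 9% | 0.3% |

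Non-uniform registration moves these figures: from July 1 2014, linear weighting towards late or early registration gives 39% or 76%. The newest main band at the 2016, 2017 and 2018 locks also shows about 58% under the July 1 2014 assumption.

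**3. XP_SV at the same lock.** Assume the 62 continuing patients are complete and the other 300 - 62 = 238 registered uniformly from March 7 2013 to December 31 2014 (five years before that arm's period ends). The observed share is 0.972 for the new patients and (238 x 0.972 + 62)/300 = about 98% overall, so 3.0% prints as about 2.9%. Equal true rates would therefore print as about 2.9% and 1.7%.

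**4. After full follow-up.** Only attrition is left. With 10, 20 or 30% assumed lost by year 5, the number at risk at the start of year 5 is 100 x (1 - loss)^0.8 = 91.9, 83.7 or 75.2. Three events per 100 registered print as 3.0%, against 3.3, 3.6 or 4.0% of those at risk.

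**5. Band overlap.** For discharge on day d, band 1 covers days 0 to 3 and band 3 starts on day d + 1. Shared days are 1-3 for d = 0, 2-3 for d = 1, day 3 for d = 2, and none for d of 3 or more.

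**The case against.** The strongest reply is that the SAP may already intend band-specific denominators. Only frozen cards enter a lock and cards are counted per binder, so a rate could be taken over patients whose binder for that year is in. That reading is compatible with the text, and a reader should not infer that the SAP positively requires mid-band patients in the denominator. But the freezing rule is written for cases, binders are mentioned only for Table 2, and no section applies either to the rates. The gap stands.

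The size is also less certain than a single figure suggests:
- It assumes that events reach the database before that year's binder does. If only completed yearly cards supplied events, over the full arm, 3.0% would print as 3.0% x 0.155 = about 0.5%. If the denominator were also per binder, there would be no dilution.
- Nominal anniversaries ignore the 30-day windows in SAP 3.2. With an early 5-year visit, registration up to October 5 2014 could count as complete: 97/432 = 22.5% rather than 15.5%.

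Table 19 has no band list, so its rates may be cumulative; the point reaches it only if they are by interval.

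A reader might infer that the final five-year results are biased in the same way. They need not be: the listed locks serve periodic reports, and with registration ending on target the last nominal five-year date is September 5 2020, inside the surveillance period. Nor does the SAP specify a between-arm test of event rates.

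A reader might also take the Occurrence Rate on Forms 3 and 3-2 for a misstated patient incidence. The formula there is explicit (events over cases) and the number of affected cases has its own line, so it is not an error.

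**Conclusion.** The concern holds as an undefined denominator. SAP 3.2 and 2.1, read as written, divide rates for late Table 18 bands by the whole arm, and nothing else in the SAP replaces that rule. The consequence is rates that are too low at interim locks, unequally by arm. In the illustration an assumed 3.0% prints as about 1.7% for XX_SV at the September 2019 lock, with about 0.3% to 1.8% across the start dates tried. Accrual pattern, event rate and capture of events are assumptions, so this range is not a bound. Once five-year follow-up is complete the effect shrinks to attrition: 3.0% against about 3.3-4.0% for an assumed 10-30% loss.

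The overlap of Table 18 bands 1 and 3 follows directly from the definitions. It concerns only discharge on days 0-2 and matters mainly if bands are added. Its frequency is unknown because the documents give no length of stay.

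This should be corrected; it does not touch the sample size or its power.

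**What to change.** 1. In SAP 3.2, define the numerator as patients with at least one event, counted once per band. For Tables 18 and 19, use as denominator the patients who entered the interval under follow-up, and print that number by arm.
2. At periodic locks, report cumulative incidence censored at last contact or data lock, with any death not included in the endpoint as the competing event. Entry alone does not cure an open band: in the July 1 2014 illustration 99.8% of XX_SV patients have entered the year 4-5 band at the 2019 lock but only 15.5% have finished it. Censoring keeps the known events from open bands, which limiting the table to finished bands would discard.
3. Exclude never-implanted patients from these follow-up denominators. Protocol 2.2 registers them but requires no follow-up. Their device deficiencies and any captured stent-related events stay in the other outputs.
4. State whether Table 19 is by interval or cumulative.
5. In Table 18, write band 1 as procedure date to 3 days after it (plus sign only), and start band 3 at the later of procedure date + 4 days or discharge date + 1 day. This leaves neither overlap nor gap.

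Cost: SAP wording, one flag and slightly more programming, with no new data. Late rates may look less favourable, and estimates for the newest band at each lock will rest on visibly fewer patients.
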